LVD	Left Ventricular Dysfunction
LVEF	Left Ventricular Ejection Fraction
MACE	Major Adverse Cardiovascular Events
MI	Myocardial Infarction
NP	Nurse Practitioner
PA	Physician Assistant
PHI	Protected Health Information
PI	Principal Investigator
US	United States
USA	United States of America

1. STUDY SUMMARY

Title	Home Telemonitoring In Patients after Myocardial Infarction Experience, HELP ME trial.
Methodology	
Randomized, parallel-group clinical trial in acute coronary syndrome patients which have undergone coronary angiography with two study groups:
 
Group 1: Discharged home with standard medical treatment.
 
Group 2: Discharged home with standard medical treatment and 12 lead ECG telemonitoring device for 90 days.

Overall Study Duration	2 years
Subject Participation Duration	90 days
Single or Multi-Site	Single Site Mayo Clinic Rochester, MN
Objectives	
Several retrospective studies indicate that patients with ACS post PCI have less readmissions and better survival with 12 lead ECG telemonitoring at home. So far, no prospective study was done to show this benefit.
 
The objective of the current study is to evaluate the incidence of ED visits, re-hospitalizations and major adverse cardiovascular events (MACE including cardiovascular death and hospitalization for myocardial infarction, unstable angina, repeat revascularization, heart failure, stroke, arrhythmias, and cardiac arrest), and cost-effectiveness over a period of 90 (+/- 7) days after an index hospitalization for an acute myocardial infarction (MI).
 
Our central hypothesis is that 12 lead ECG home telemonitoring decreases general and cardiac ED presentation and hospital readmission rates without an increase in MACE and at a lower health care utilization cost compared to patients with standard therapy alone.
 
Three specific aims will be pursued:
 
Aim 1: To compare the rates of ED visits and re-hospitalization rates as well as related downstream cardiovascular testing (echocardiogram, stress test or coronary CT, or invasive coronary angiogram) from discharge after index hospitalization for MI to 90 days follow-up between patients undergoing standard care alone or standard care plus the home 12 lead ECG telemonitoring device
 
Aim 2: To compare the rates of MACE from discharge after index hospitalization for MI to 90 days follow-up between patients undergoing standard care alone or standard care plus the home 12 lead ECG telemonitoring device
 
Aim 3: To compare health care cost utilization from discharge after index hospitalization for MI to 90 (+/-7) days follow-up between patients undergoing standard care alone or standard care plus the home 12 lead ECG telemonitoring device

Number of Subjects	240 patients in total, enrolled over one-two years

Inclusion and Exclusion Criteria	
Inclusion criteria:
 
 • ≥18 years of age, • Acute myocardial infarction, both STEMI and non-STEMI • Able to use the home ECG telemonitoring • Must have smartphone device with home wi-fi/mobile internet which allows 24/7 ability to transmit ECG • Caring family member who will be able to help/perform the ECG in case the patient himself won't be able to do it • Planned to be discharged home by the treating team 
Exclusion criteria:
 
 • No ability to use the device at home • No smartphone device or home wi-fi/mobile internet which prevent 24/7 ability to transmit ECG • Cannot download the smartheart app • No support in home environment • Out of hospital cardiac arrest: secondary to a non-shockable rhythm, unrelated to an acute coronary syndrome, or with any level of neurologic damage. • Resident of nursing home or acute care facility • Uninterpretable ECG at discharge – left bundle branch block (LBBB), pacemaker or implantable cardioverter defibrillator (ICD) with pacing dependence. • Patients who are planned for staged PCI after the index hospitalization
Study Product, Dose, Route, Regimen	Prior to discharge patients will be 1:1 randomized to standard medical therapy or standard medical therapy + 12 lead ECG Smartheart telemonitoring device.
Duration of Administration	Patients will receive the device for the period of 90 (+/-7) days .
Reference therapy	Group 1 will serve as the reference group
Statistical Methodology	Inter-group differences in the rates of the primary combined endpoint will be analyzed by the Chi square test.

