4.2 Study Rationale

This study will be pursued as a prospective clinical trial building upon and extending the available evidence of the use of outpatient ECG monitoring after MI outlined above. We will test the clinical and economic impact of the SHL-telemonitoring cardiac device during the first 90 days after MI in a defined health care environment. The current standard of care is antiplatelet agents, beta blockers and statins alone, with a reported re-hospitalization rate of 17-25%. In addition to the standard care, patients in the intervention arm will be instructed on how to use the device and send ECG to a Mayo Clinic CICU designated study NP/PA, which will be in communication with the participant to respond to recordings taken for symptom review. Patients with a *true* acute cardiac event will be advised to seek medical assistance immediately, in case of STEMI, VT/VF or CAVB the EMS will be sent to the participant. Patients with reassuring ECG and low suspicion of acute cardiac event will be advised to postpone medical assistance and to avoid unnecessary emergency department [ED] visits. Such an approach may improve patient outcomes and reduce costs at the same time. Additionally, the COVID-19 pandemic brought its challenges to the health systems worldwide, those are uncertain times and prevention of unnecessary ED visits and readmissions after discharge would be beneficial, in particularly for patients post AMI having comorbidities.

[figure not shown]
It is important to emphasize that the device is safe to use and this is a very low risk study with a large potential benefit of decrease in unnecessary readmission rates, subsequent costs and early detection of real cardiac abnormalities with prompt medical assistance could improve outcomes. This study is planned to address the importance of home telemonitoring in cardiac patients and could have future implications on the current guidelines and standard care.

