9.2. Sample Size and Randomization

Patients will be randomized to either standard medical therapy or the medical therapy plus the Smartheart 12 lead ECG home device.

The primary combined endpoint parameter is the rate of ED visits/rehospitalizations as well as related downstream cardiovascular testing (echocardiogram, stress test or coronary CT, or invasive coronary angiogram) at 90 (+/-7) days after discharge and mortality rates during the 90 (+/-7) days of follow up. Based on the most recent in-house registry data, we have about 50 AMI patients undergoing PCI a month. Accordingly, we have at least 600 patients a year who are discharged with a diagnosis of AMI from Saint Mary's Hospital.

Our own registry data further indicate that 24% of revascularized AMI patients will present to the ED or will be readmitted within 90 days. This is in keeping with the published literature citing a rate of 20-30%. Half of these patients will present for cardiovascular complaints and may get further testing, including echocardiogram, stress test or coronary CT, or invasive coronary angiogram. Having a 12-lead ECG available and the phone triage available to direct care may impact not only emergency presentation but also downstream testing. This will be considered in this trial, and each of these will be considered as a component to the combined primary endpoint event. Assuming that patients presenting with cardiovascular concern may receive two of the outlined downstream test as they present to the ED and hospital, the estimated event rate will be 48%. With 120 patients in each arm the study we would be adequately powered (beta error <0.2) to show a statistically significant (at alpha error levels of <0.05) for a 37.5% event reduction.

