9.5.2.1. Outcome measures

- Rate of ED visit and rehospitalization, overall and related to cardiovascular and non-cardiovascular causes
- Rate of downstream testing modalities (echocardiogram, stress test or coronary CT, or invasive coronary angiogram)
- Rate of MACE as defined above
- Amount of money in US dollars that was spent for any medical service related to cardiovascular and non-cardiovascular diseases in both study groups.
- Quality of life questionnaire score in both study groups at the time of enrollment and at 90 days.

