9.6. Data Analyses

The primary analysis for Aim 1 (lead aim of the study) will be a comparison of the rates of the primary combined endpoint between group 1 and 2 via Chi square test for categorical data of independent samples. The test will be used for any other categorical data. For continuous data, an independent groups t-test or Wilcoxon as appropriate after testing distributional assumptions.

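### The summary hypothesizes no increase in MACE, but the only analysis planned for MACE is a chi-square test of difference, which cannot support that clause

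*Combined protocol and SAP*

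**What the plan says.** The central hypothesis in section 1 (Study Summary, Objectives) is that the device strategy "decreases general and cardiac ED presentation and hospital readmission rates without an increase in MACE", and at lower cost. The aim attached to it is neutral: "Aim 2: To compare the rates of MACE from discharge after index hospitalization for MI to 90 days follow-up". Section 3.2(c) repeats that aim, and section 9.5.2.1 lists "Rate of MACE as defined above" among the secondary outcomes.

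Section 9.6 compares the primary composite "via Chi square test for categorical data of independent samples" and then adds: "The test will be used for any other categorical data". MACE is a yes/no outcome, so this sentence is its whole analysis plan. The documents give no confidence interval, margin, expected rate or power for MACE.

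The sample size in section 9.2 concerns the primary composite only: "With 120 patients in each arm the study we would be adequately powered (beta error <0.2", "at alpha error levels of <0.05) for a 37.5% event reduction". The re-estimation in section 9.4 uses rehospitalizations and ED visits in the device arm, not MACE.

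Section 9.1 states the primary hypothesis differently, as fewer ED visits and rehospitalizations and therefore lower cost. It has no MACE clause and mentions lower mortality only as a possible further benefit. Sections 5 and 9.4 call the study a pilot.

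Under section 4.2, device patients whose ECG is reassuring and in whom suspicion of an acute cardiac event is low "will be advised to postpone medical assistance and to avoid unnecessary emergency department [ED] visits".

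**The concern.** A no-increase clause is a no-worse-than statement. It is supported by an interval whose upper end is acceptably low, not by failure to reject equality. The plan supplies only a test of equality, so no result it can produce answers the clause.

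The clause is not ornamental. The expected benefit (fewer presentations) and the possible harm (an event recognized late) arise from the same triage advice. A fall in ED visits is hard to interpret without knowing how large a rise in MACE the data leave open. At this sample size, a clinically important rise could easily accompany a p-value above 0.05.

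**Working it through.** **The plan's own figure.** Section 9.2: control rate 48%, 37.5% reduction, so the device rate is 0.48 × 0.625 = 30%, with 120 per arm and alpha 0.05 (taken as two-sided). For a two-proportion test with pooled variance:

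- s0 = √(2·p̄(1−p̄)/n), where p̄ is the mean of the two rates
- s1 = √((p0(1−p0) + p1(1−p1))/n)
- power = Φ((d − 1.96·s0)/s1) + Φ((−d − 1.96·s0)/s1), where d is the absolute difference

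With p̄ = 0.39, s0 = 0.0630 and s1 = 0.0619, power = Φ((0.18 − 0.1234)/0.0619) = 0.82. The stated power reproduces for the composite. Nothing comparable exists for MACE.

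**Assumed MACE rate.** None is stated. Section 9.2 gives 24% returning to the ED or being readmitted within 90 days, half with cardiovascular complaints: 0.24 × 0.5 = 12%. This is a loose guide, since a cardiovascular complaint is not necessarily a MACE. The range used is 5% to 20%.

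**Expected precision with equal rates.** Half-width = 1.96·√(2p(1−p)/n). At 10% and n = 120: 1.96·√(0.18/120) = 7.6 points. The example enlargement in section 9.4, 181 per group, gives 1.96·√(0.18/181) = 6.2 points.

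**Chance that a true increase is non-significant** (1 − power, n = 120). For 12% to 18%: p̄ = 0.15, s0 = 0.0461, s1 = 0.0459, and (0.06 − 0.0904)/0.0459 = −0.66. Power is 0.255, so 75% of such trials are non-significant.

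| Control MACE (assumed) | 95% half-width, 120 per arm | True 50% increase non-significant | True doubling non-significant |
|---|---|---|---|
| 5% | ±5.5 points | 87% | 69% |
| 10% | ±7.6 points | 78% | 42% |
| 12% | ±8.2 points | 75% | 32% |
| 20% | ±10.1 points | 57% | 7% |

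The same formula with 181 per arm gives 83%, 70%, 64% and 41% for the 50% increase.

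**What a non-significant table can look like.** 14 of 120 against 25 of 120 (11.7% and 20.8%, risk ratio 25/14 = 1.79): the difference is 0.0917, the pooled standard error is √(2 × 0.1625 × 0.8375/120) = 0.0476, z = 1.92 and p = 0.054. The Newcombe 95% interval runs from −0.2 to +18.5 points.

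**What equal true rates look like.** With true rates equal at 8% to 12%, exact enumeration of two binomials of 120 puts the Newcombe upper limit above +5 points in about 73% to 78% of trials. At 10% it lies above +8 points in about 48%.

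**The case against.** The strongest reply is that the plan commits no error of inference. A reader might infer that p > 0.05 on MACE will be reported as proof of safety and so complete the hypothesis. The documents do not say this. Aim 2, section 3.2(c) and section 9.5.2 only compare MACE rates, and section 9.6 names a test without a rule for a null result. That reply stands against the stronger reading. It does not remove the gap: the summary states a no-increase hypothesis, and no other criterion is offered for it.

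Second, MACE is secondary, the study is called a pilot, and section 9.1 omits MACE from the primary hypothesis. This stands and limits the seriousness: no sample size or success rule depends on MACE. It also means that the summary and section 9.1 differ and should be aligned.

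Third, the trial does not tell device patients in general to postpone care. Section 4.2 limits that advice to a reassuring ECG with low suspicion, directs patients with a true acute event to immediate help, and sends EMS for specified findings. This stands. The possible harm is confined to patients triaged as low risk.

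Fourth, the size of the problem depends on an unstated rate and on 120 per arm. At 20% MACE a doubling would be detected with about 93% power, and an enlarged trial would be more precise. This stands as a limit on the numbers. At 120 per arm, missing a 50% increase is still the likelier result at every rate checked.

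**Conclusion.** The point holds in this form: the summary contains a no-increase clause for MACE, and the plan has no analysis that could support it. It is a moderate point that should be fixed, not one that undermines the primary comparison.

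With 120 per arm and an assumed control MACE rate of 5% to 20%, a true 50% increase goes undetected in about 57% to 87% of trials. The 95% interval with equal rates is about ±5.5 to ±10 points. Both figures improve if section 9.4 enlarges the trial.

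Two stronger readings should be avoided. The documents do not show that the sponsor will treat non-significance as safety. Nor is there a fixed increase, such as 8 points at 10% MACE, that the trial can or cannot exclude. The upper limit depends on the observed difference, and the half-width is only expected precision.

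**What to change.** In section 9.6, add that MACE will be reported as a risk difference (device minus control) with a two-sided 95% confidence interval by the Newcombe or Miettinen-Nurminen method. The conclusion should be drawn from the upper limit rather than the p-value, and a non-significant test should not be reported as no increase. State the expected precision, for example about ±7.6 points at 10% MACE with 120 per arm, and label the rate as an assumption.

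In the Study Summary, align the hypothesis with section 9.1 by replacing the no-increase clause with an aim to estimate the difference in MACE. If the sponsor keeps the claim, a justified margin must be fixed before any outcome is seen.

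For scale, n per arm = (1.96 + 0.84)²·2p(1−p)/margin² (one-sided 0.025, 80% power, equal true rates). An illustrative 5-point margin needs 299, 664 and 1005 per arm at MACE of 5%, 12% and 20%; a 10-point margin needs 75, 166 and 252. Estimation is therefore the realistic choice at this size.

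The cost is a few sentences, with no extra patients, visits or data. The downside is a more modest safety statement.

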3. STUDY OBJECTIVES

3.1 Primary Objective

The primary objective of this trial is to compare the rates of ED visits and re-hospitalization rates as well as related downstream cardiovascular testing (echocardiogram, stress test or coronary CT, or invasive coronary angiogram) from discharge after index hospitalization for MI to 90 (+/-7) days follow-up between patients undergoing standard care alone or standard care plus the 12 lead ECG Smartheart home telemonitoring device.

3.2 Secondary Objectives

The secondary objectives of this study are:

- a) To compare the rates of cardiovascular and non-cardiovascular ED visits and re-hospitalizations rates, from discharge after index hospitalization for MI to 90 (+/-7) days follow-up between patients undergoing standard care alone or standard care plus the 12 lead ECG Smartheart home telemonitoring device.
- b) To compare the rates of downstream cardiovascular testing (echocardiogram, stress test or coronary CT, or invasive coronary angiogram) from discharge after index hospitalization for MI to 90 (+/-7) days follow-up between patients undergoing standard care alone or standard care plus the 12 lead ECG Smartheart home telemonitoring device.
- c) To compare the rates of MACE from discharge after index hospitalization for MI 90 (+/-7) days follow-up between patients undergoing standard care alone or standard care plus the 12 lead ECG Smartheart home telemonitoring device.
- d) To compare health care cost utilization (including all cardiovascular inpatient and outpatient office visits and tests) from discharge after index hospitalization for MI to 90 (+/-7) days follow-up between patients undergoing standard care alone or standard care plus the 12 lead ECG telemonitoring device.
- e) To compare quality of life (MacNew Heart Disease Questionnaire) from discharge after index hospitalization for MI to 90 (+/-7) days follow-up between patients undergoing standard care alone or standard care plus the 12 lead ECG telemonitoring device.

4. BACKGROUND AND RATIONALE

4.1 Background

Survivors of a first acute myocardial infarction (AMI) face a substantial risk of further major adverse cardiovascular events (MACE), including death, recurrent MI, heart failure, arrhythmias, angina, and stroke. The rate of rehospitalization within 30 days after acute MI is reported to range between 17 and 25 percent [1,2]. In a single-community study, Olmsted County, Minnesota, United States, of 3010 patients who were hospitalized for a first-ever MI (STEMI – 31%) rehospitalization within 30 days occurred in about 19 percent [3]. Across the broad spectrum of patients with acute myocardial infarction (MI), short-term (in-hospital or 30-day) mortality has been decreasing over the past 30 years, concomitantly with the increasing use of reperfusion strategies and proven preventative therapies such as beta blockers, aspirin, and statins [4-12]. The 30-day mortality after all acute coronary syndromes (ST-elevation myocardial infarction [STEMI], non-ST elevation myocardial infarction [NSTEMI], and unstable angina) is less than 5 percent [13]. The incidence of SCD after acute MI is the same with STEMI and NSTEMI [4,14]. Among patients who have had an MI and are followed for about four years, approximately one-half of sudden deaths occur in the first year and one-quarter in the first three months [15,16]. The risk is markedly increased in patients with a left ventricular ejection fraction ≤ 35 percent. Additional important aspect following acute MI [AMI] is financial, although mortality attributable to AMI has declined, 30-day post-AMI readmission rates remain high (median 19.9%) and carry a heavy economic burden, accounting for 21,000 admissions at a cost of 136 million dollars in the United States [17].

“SHL”-Telemedicine is a call center that was established in 1987 in Israel. It operates 24 hours/day, 365 days a year, and is managed by a medical staff. Each subscriber’s medical file (which also includes a full 12-lead

electrocardiogram [ECG]) is electronically stored and continuously updated. The subscribers carry a SmartHeart 12 lead ECG device by which they can transmit a full 12-lead ECG via internet by a designated smart application and call the SHL center, the archived information is uploaded within seconds on a monitor together with the real-time transmitted information, and the staff evaluates the caller's medical status according to the transtelephonic anamnesis, newly transmitted ECG data, and pertinent facts from the electronic file. By integrating computerized algorithms and clinical judgment, the staff advises the subscriber which steps to take and which action the staff will take according to predefined standing orders and protocol [18]. Several retrospective studies showed favorable clinical outcomes of patients using "SHL"-Telemedicine and Smarheart device, including reduction in a 30-day readmission rate, shorter time lag between the onset of symptoms and contacting medical assistance and lower mortality rates[18-20].

4.2 Study Rationale

This study will be pursued as a prospective clinical trial building upon and extending the available evidence of the use of outpatient ECG monitoring after MI outlined above. We will test the clinical and economic impact of the SHL-telemonitoring cardiac device during the first 90 days after MI in a defined health care environment. The current standard of care is antiplatelet agents, beta blockers and statins alone, with a reported re-hospitalization rate of 17-25%. In addition to the standard care, patients in the intervention arm will be instructed on how to use the device and send ECG to a Mayo Clinic CICU designated study NP/PA, which will be in communication with the participant to respond to recordings taken for symptom review. Patients with a *true* acute cardiac event will be advised to seek medical assistance immediately, in case of STEMI, VT/VF or CAVB the EMS will be sent to the participant. Patients with reassuring ECG and low suspicion of acute cardiac event will be advised to postpone medical assistance and to avoid unnecessary emergency department [ED] visits. Such an approach may improve patient outcomes and reduce costs at the same time. Additionally, the COVID-19 pandemic brought its challenges to the health systems worldwide, those are uncertain times and prevention of unnecessary ED visits and readmissions after discharge would be beneficial, in particularly for patients post AMI having comorbidities.

[figure not shown]
It is important to emphasize that the device is safe to use and this is a very low risk study with a large potential benefit of decrease in unnecessary readmission rates, subsequent costs and early detection of real cardiac abnormalities with prompt medical assistance could improve outcomes. This study is planned to address the importance of home telemonitoring in cardiac patients and could have future implications on the current guidelines and standard care.

